Immune and Other Microbial Biomarkers - blood, induced sputum, nasal epithelial lining fluid (NELF), stool, exhaled air

- Serum total IgE and specific IgE to aeroallergen panel (ImmunoCap)
- Complete blood count with cell differential
- Sputum cell differential counts
- Sputum, NELF cytokines (Mesoscale Discovery; 30-plex panel: Eotaxin, Eotaxin-3, GM-CSF, IFN- γ , IL-10, IL-12/IL-23p40, IL-12p70, IL-13, IL-15, IL-16, IL-17A, IL-1 α , IL-1 β , IL-2, IL-4, IL-5, IL-6, IL-7, IL-8, IL-8 (HA), IP-10, MCP-1, MCP-4, MDC, MIP-1 α , MIP-1 β , TARC, TNF- α , TNF- β , VEGF-A)
- Sputum antimicrobial peptide expression (RT-PCR): defensins, lysozyme, lactoferrin, LL-37, and secretory leukocyte protease inhibitor
- Total bacterial burden in sputum samples by 16S rRNA Q-PCR or droplet digital PCR; with determination of both relative and absolute abundances of taxa.
- Respiratory microbial functional gene annotations from metagenomic sequencing
- Fecal metabolites by global/untargeted and targeted short-chain fatty acid assays

Primary hypotheses:

Hypothesis 1. Dupilumab-induced suppression of T2 inflammation in severe asthma is associated with changes in respiratory tract bacterial burden at 1 month and 4 months after treatment initiation (16S rRNA qPCR of bacterial DNA in induced sputum)

Hypothesis 2. Dupilumab-induced suppression of T2 inflammation in severe asthma is associated with changes in the compositional structure of respiratory and/or gut microbiota, detectable at 1 month and 4 months after initiation of treatment. (bacterial and fungal microbiota profiles and related measures of microbial diversity in induced sputum and stool)

Hypothesis 3. Dupilumab-induced changes in specific biomarkers (e.g. T2 and non-T2-related cytokines; targeted gene expression) correlate with changes in the respiratory and/or gut microbiome (phylogenetic diversity, specific compositional and functional profiles)

Hypothesis 4. Dupilumab-related improvement or lack of improvement in clinical outcomes (lung function, asthma control scores) over a 4-month period are associated with changes in specific characteristics of the respiratory and/or gut microbiome.

IV. STUDY OVERVIEW, INCLUSION/EXCLUSION CRITERIA, PROCEDURES

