Dupilumab-eligible severe asthma patients will be identified and recruited from asthma and allergy clinics at the University of Michigan. Severe asthma patients are seen and cared for by Pulmonary and Allergy faculty at two main outpatient clinic locations. All severe asthma patients who meet clinical prescribing criteria for dupilumab are considered eligible and will be recruited for this study. The study coordinator and/or physician investigator will meet with subjects to provide information about the study and invite them to participate in this 3-visit study occurring over a 4-month period. We will enroll 15 severe asthma patients who complete all 3 visits. The funder of the grant for this project (Regeneron) will provide dupilumab for this study.

Inclusion criteria:

1. Adults ages 18 or older with physician-diagnosed/-managed severe asthma who are clinically eligible for dupilumab (clinical criteria below).
2. Current treatment with a medium-to-high-dose inhaled glucocorticoid (fluticasone propionate at a total daily dose of ≥ 440 μ g or equipotent equivalent) plus up to at least one additional controller (e.g., a long-acting β 2-agonist or leukotriene receptor antagonist)
3. Eosinophilic asthma phenotype (blood eosinophil level >300) or asthma requiring daily oral corticosteroids
4. Asthma that is uncontrolled, as defined by a score on the Asthma Control Test of 19 or lower, OR a worsening of asthma in the past year that led to an asthma hospitalization, ED visit, or 3 days of oral corticosteroids
5. Severity of asthma that, in the opinion of the subject's asthma care specialist, requires dupilumab for control

Exclusion Criteria:

1. Patients with diagnosis of other chronic lung diseases (e.g. COPD, idiopathic pulmonary fibrosis, Churg-Strauss syndrome, ABPA, etc.)

2. Current smoker or reported smoking within 1 month of the screening visit (tobacco or any inhaled recreational product)
3. Greater than 10 total pack-year of cigarette smoking history
4. Treatment with oral corticosteroids for an asthma exacerbation 1 month prior to screening or during the screening period
5. Use of any biologic therapy for asthma within the past 3 months
6. Respiratory or GI illness within 1 month prior to screening or during the screening period
7. Treatment with antibiotics for acute infections within six weeks prior to screening or during the screening period.
8. Pregnancy at enrollment or during the study
9. Known hypersensitivity to dupilumab or its excipients

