4. Study coordinator must don appropriate protective personal equipment (PPE) for the study visit and keep on during the duration of the visit (gloves, masks, safety goggles or face shield for eye protection; corrective glasses do not suffice).
5. If not previously collected, obtain signed informed consent from the subject. Confirm no changes in continued eligibility of subject since screening, review inclusion/exclusion criteria (*study coordinator or physician time: 5-10 min*).
6. Perform procedures as listed in **Table 1**. Plan the order of procedures accordingly with the following performed by the study coordinator. Questionnaires should be completed first (*time: 10 minutes*). FeNO measurement (*time: 3-5 minutes*) and NELF collection (*time: 10 minutes*) should be performed next, before spirometry pre- and post-bronchodilator (*time: 45 minutes including 15min wait pre-/post-bronchodilator*), oral rinse/tongue scraping collection (*time: 2 minutes*), and sputum induction (*time: 15 minutes*). Blood draw at phlebotomy lab (*time: 5 min*) can be done anytime during the visit.
 - **FeNO measurement** will be performed using NiOx Vero machine per device instructions.

- **NELF collection** (instructions and schematic of sample collection provided by UNC [name] Lab/Spirovation; Appendix 4)
 - The NELF procedure involves sitting the patient comfortably upright, and the head extended backwards
 - Place the absorbent end of the nasosorption strip device on the lateral wall of the nasal cavity, onto the lateral/inferior surface of the inferior turbinate
 - Hold the strip in place by pressing a finger against the nostril for 60 seconds to absorb nasal secretions
 - Remove the device (moist with nasal mucosal lining fluid) from the nostril and place it on wet ice until storage
 - Repeat these steps in the other nostril using a fresh nasosorption strip

7. Perform spirometry pre- and post-bronchodilator. Collect oral rinse/tongue scraping sample, then perform sputum induction assuming the subject's post-bronchodilator FEV₁ meets safety criteria per Sputum Induction MOP. Record lung function (FEV1) every 2 minutes per protocol during sputum induction. Notify [name] lab personnel when specimens are ready for pick-up.

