5. *NELF sample collection.* The purpose of collecting nasal epithelial lining fluid is that it is a simple non-invasive way of sampling the respiratory mucosa to measure immune cytokines. NELF has been used in a number of research investigations to profile mucosal immune mediators relevant to asthma.
6. *Spirometry pre- and post- bronchodilator.* A standard clinical test for the presence of airflow obstruction and assessment for reversibility. FEV1 and FVC will be determined before and after 4 puffs of albuterol. This will be performed by experienced study coordinators using existing equipment for research use.
7. *Blood draw:* This will be performed by a clinical phlebotomist or nursing staff
8. *Complete blood count (CBC) with differential.* Results will be used to determine peripheral blood eosinophil counts, to gauge biological response to treatment.
9. *Total and specific IgE.* Clinical tests of allergy-related immune responses. We will measure both total serum IgE and respiratory allergen specific IgE based on ImmunoCap assays
10. *Plasma* will be stored at -80°C for future analysis of other immune or metabolic response markers.
11. *Oral saline rinse/tongue scraping:* This involves having the subject swish and gargle 10mL of sterile saline than spit into a collection container. This is followed by applying a commercially available plastic tongue scraper to remove any film on the tongue into the same collection container. This is performed prior to sputum induction and will be processed for microbiome analyses as biological controls.
12. *Sputum induction:* This will follow a standardized manual of procedures involving inhalation of 3% saline mist for 12 minutes. Subjects will be instructed to periodically cough up sputum into a specimen cup and FEV1 is monitored every 2 minutes using a handheld PiKo-6 meter per a standardized protocol. If the FEV1 declines ≥20% of baseline, the procedure would be stopped and albuterol administered with follow-up monitoring. The sputum will be portioned into aliquots to be processed for different analytic purposes, including cell count/differential analysis, microbial community profiling, mediator analyses.
13. *Stool sample collection.* This will be processed for analysis of gut microbiome composition and intestinal metabolites and their relationships to clinical measures of treatment response.

VII. Recruitment

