Subject with severe asthma who are clinically eligible for potential treatment with dupilumab will be recruited from pulmonary asthma and allergy clinics at the University of Michigan. Identified eligible patients will be screened by the study coordinator to confirm eligibility and interest in participating.

VIII. Human Subjects and Risks

A. Subjects:

1. General Description: inclusion/exclusion criteria are as described earlier in this document.
2. Gender/Minority Inclusion: No subject will be excluded based on gender or ethnicity.
3. Exclusion of children: Children (<18 years of age) are excluded from this study as the research aim relate to hypotheses about the effects in adult asthmatics of dupilumab treatment on host-microbiome interactions and clinical outcomes.

B. Potential Risks and Procedures for Minimizing Risks: Potential risks can be categorized as “Likely”, “Infrequent”, or “Rare”.

Likely Risks

- ***Venipuncture risks:*** Drawing blood may cause temporary discomfort from the needle stick, bruising, and infection. Dizziness may occur and subjects may be asked to lie down for venipuncture if they indicate this history.
- ***Spirometry/peak flow risks:*** Breathing fast and hard into a spirometer or peak flow device can be associated with cough or lightheadedness. Such symptoms are usually temporary and resolve within a few minutes without intervention.
- ***Albuterol use risks:*** Albuterol is an approved drug that broncho-dilates the airways and widely used to treat asthma symptoms. Albuterol use may cause muscle tremors, palpitations, rapid heart rate, and headache. If these symptoms do occur, they are temporary and usually disappear within 1 hour.
- ***Sputum induction risks:*** The sputum induction manual of procedures for this study is adapted from those used in prior NHLBI asthma clinical research studies. The risks associated with this test include an unpleasant taste in the mouth, asthma-like symptoms (chest tightness, wheezing, shortness of breath), and occasionally nausea. Infrequently, the procedure may result in an asthma exacerbation requiring treatment. To prevent asthma-like symptoms, all subjects will have received 4 puffs of albuterol prior to undergoing induction. FEV1 will be monitored during the procedure which may be terminated for sustained decline in FEV1. Additional albuterol can be administered per to reverse bronchoconstriction which is rarely refractory to additional albuterol.

Infrequent Risks

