To address our exploratory hypotheses in this pilot study, we will first generate the following readouts of microbial community composition: (1) read counts or relative abundance data for each microbial species determined from sequence alignments to reference databases. These readouts can be at the level of ASVs (amplicon sequence variant) or OTUs (operational taxonomic unit), which can also be collapsed into higher taxonomic levels for analysis, e.g. genus or family-level comparisons; (2) within-sample and between-sample measures of microbial diversity, i.e. alpha- or beta-diversity. Alpha-diversity measures will include Shannon, inverse Simpson, richness, and the phylogeny-based Faith index. Beta-diversity measures will include calculation of Bray-Curtis and Unifrac distance measures, the latter being a phylogeny-based calculation of between-sample differences in overall microbial composition. We will also determine 16S rRNA gene copy numbers in induced sputum by quantitative PCR, which serves as a proxy measure of 'bacterial burden' often used in the airway/lung microbiome literature. Other generated molecular data will be used to explore secondary questions related to whether dupilumab intervention effects change in predicted microbial functions (KEGG orthologue modules and pathways), intestinal metabolites, and whether changes in the airway or gut microbiome correlate with changes in inflammatory markers and immune mediators measured in sputum, blood and NELF.

For Hypothesis 1, we will compare sputum bacterial burden (normalized 16S rRNA gene copy number) before and after treatment (baseline vs month 1; baseline vs. month 4; all three timepoints), using paired t-test if normally distributed (Wilcoxon sign-rank test if non-normal distribution) and repeated measures ANOVA for all three timepoints.

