For Hypothesis 2, we will compare alpha-diversity measures before and after treatment (baseline vs month 1; baseline vs. month 4; all three timepoints), using paired t-test, Wilcoxon sign-rank test or rm-ANOVA. For beta-diversity -based measures of overall microbial composition, we will use Bray-Curtis or Unifrac distance matrices to perform (i) pairwise PERMANOVA tests (R package vegan; adonis2 or in QIIME2 (q2-longitudinal) [20,21]; (ii) linear mixed-effects models with a random intercept and slope for each individual; (iii) Procrustes analysis with Mantel test. We will also explore other available tools for time-series microbiome analysis such as MDSINE [22]. Differences in specific species (ASVs, OTUs) between time points will be analyzed using DESeq2 which applies a variance-stabilizing transformation to the data. Other methods using log-ratio transformation (e.g., CLR) of species counts will also be explored.

For Hypothesis 3, we will examine correlations between change in biomarkers (e.g., cytokines, inflammatory cell counts, targeted gene expression) and changes in the airway or gut microbiome. The latter based on either specific compositional readouts (ASV, OTUs) or in terms of overall microbial community structure. The following approaches will be used: (i) initial correlation analyses performed between paired data at each time point (e.g., specific biomarker dataset vs. microbial ASVs), using Spearman correlations, with adjustments for multiple comparisons by q-values; (ii) linear mixed-effects models, e.g. levels of immune markers as predictors of post-treatment microbiota diversity or abundances of each microbiota member; fixed effects would include age, sex, BMI, and chronic treatments including corticosteroids or macrolides (type, dose, route); (iii) tests for biomarker association with overall microbial community structure, using distance-based PERMANOVA (adonis2) at each time point or in a paired design; (iv) additional computational approaches based on methods for high-dimensional dataset comparisons, as described below.

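### The three-timepoint repeated-measures ANOVA on sputum outcomes uses only patients with all three samples; a suitably specified mixed-model visit test would keep the rest

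*Combined protocol and SAP*

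**What the plan says.** Section XII (Data Analysis) compares sputum bacterial burden at baseline vs month 1, baseline vs month 4, and across all visits. The two-visit comparisons use a paired t-test or Wilcoxon test. The three-visit comparison uses "repeated measures ANOVA for all three timepoints". For alpha-diversity under Hypothesis 2 the comparisons are the same, "using paired t-test, Wilcoxon sign-rank test or rm-ANOVA". For these tests the section does not say what happens to a patient who lacks one sample.

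The Hypothesis 1 outcome is "16S rRNA qPCR of bacterial DNA in induced sputum" (Section III), so without sputum there is no value. Section IV sets the sample size: "We will enroll 15 severe asthma patients who complete all 3 visits". That condition concerns visits, not samples.

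An attended visit can fail to give sputum, or give too little:
- Induction goes ahead only if post-bronchodilator FEV1 "meets safety criteria per Sputum Induction MOP" (Section V, Visit 1, item 7).
- If FEV1 falls far enough, "the procedure would be stopped and albuterol administered with follow-up monitoring" (Section VI, item 12). Section VIII adds: "FEV1 will be monitored during the procedure which may be terminated for sustained decline in FEV1".
- One sample serves several assays: "The sputum will be portioned into aliquots to be processed for different analytic purposes" (Section VI, item 12).

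**The concern.** Classical repeated-measures ANOVA needs a complete set of three values per patient, and standard software either removes the incomplete patient or refuses the data. In a 15-patient pilot, each missing sample therefore takes two good ones out of the three-timepoint test.

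There is also a difference in assumptions. Complete-case ANOVA generally needs samples to be missing completely at random. A likelihood-based mixed model needs only that they be missing at random given the observed data. Neither is protected if missingness depends on values that were never observed. What is at stake is precision, and some robustness, in one of the tests listed for a primary hypothesis.

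**Working it through.** **Inputs from the documents.** 15 patients, three visits, at most 15 × 3 = 45 sputum samples. The plan states no power, effect size, SD, alpha or yield, so there is no planned figure to reproduce.

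**Assumptions.** Chance s of a usable sample per visit: 95/90/85/75%, failures independent. Total SD 1, within-patient correlation (ICC) 0.6, mean changes of 0.3 SD at month 1 and 0.6 SD at month 4, two-sided alpha 0.05.

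**Step 1: degrees of freedom.** If one patient lacks one sample, the ANOVA falls to 14 patients with error df 2 × (14 − 1) = 26. The mixed model keeps 44 samples with df 44 − 15 − 2 = 27. If four patients each lack one, the ANOVA has 11 patients and df 20; the mixed model has 41 samples and df 24.

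**Step 2: counts.** Expected patients with all three samples = 15s³. Share of obtained samples outside the three-timepoint ANOVA = 1 − s². Many of these still enter a paired test. A sample enters no planned Hypothesis 1 test only if it stands alone or if baseline is the missing one, a share of (1 − s)² + 2s(1 − s)/3. The chance that all 45 samples exist, s⁴⁵, is 10% at s = 0.95 and 0.9% at s = 0.90.

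**Step 3: power.** For the ANOVA with n complete patients, noncentrality is n × Σ(μ − mean)²/(1 − ICC) = n × (0.09 + 0 + 0.09)/0.4 = 0.45n. At n = 15 this is 6.75 on 2 and 28 df, which gives 59%. For the baseline vs month 4 paired t-test, the standardized change is 0.6/√(2 × 0.4) = 0.67, which gives 68% with 15 pairs. Below, the paired figures average over the random number of available pairs. The ANOVA and mixed-model figures come from 10,000 simulated trials per setting (REML random intercept, visit as a factor, F on 2 and samples − participants − 2 df).

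| Yield per visit | Complete patients | Outside the 3-timepoint ANOVA | In no planned H1 test | ANOVA power | Mixed-model power | Paired t, month 4 |
|---|---|---|---|---|---|---|
| 100% | 15 | 0% | 0% | 59% | 59% | 68% |
| 95% | 12.9 | 10% | 3% | 51% | 55% | 62% |
| 90% | 10.9 | 19% | 7% | 44% | 52% | 57% |
| 85% | 9.2 | 28% | 11% | 36% | 47% | 51% |
| 75% | 6.3 | 44% | 19% | 24% | 40% | 39% |

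Restricting the mixed model to patients with at least two samples gives 55/52/47/39%. The gain therefore comes from patients with two samples, not from single-sample patients.

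**Step 4: range.** ANOVA vs mixed model at 90/85/75% yield:
- ICC 0.4: 32/25/17% vs 38/34/28%.
- ICC 0.8: 72/64/44% vs 81/77/67%.
- Failures clustered within patients (correlation 0.3): 49/41/32% vs 54/49/42%.

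**Step 5: type I error.** With samples missing completely at random, the joint test rejects 5.0–6.0% of the time and the ANOVA 5.0–6.1%, including settings with unequal correlations between visits. As a stress test, 3,000 null data sets (15 patients, correlation 0.6) made month 4 missingness depend strongly on the observed month 1 change. Complete-case ANOVA rejected 21% of the time and the mixed model 4.9%. This illustrates the difference in assumptions; it does not forecast this trial.

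**Step 6: when the two tests agree.** With complete data, compound symmetry with an unbounded intercept variance reproduced the ANOVA F in all 500 data sets at each correlation tried (0, 0.3, 0.6). Holding the variance at zero or above breaks the equality in about 5% of data sets at correlation 0.3, and 0.1% at 0.6. In one example the ANOVA p-value was 0.0062; a chi-square Wald test gave 0.0022 and an unstructured (Hotelling-type) test 0.0265.

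**The case against.** The strongest reply is that the loss may be small or nil. Section IV requires 15 patients with all three visits, and Table 1 schedules induction at each one. An induction stopped early may still give a sample. The induction manual, which may contain a repeat rule, is not among the documents. All of this stands: the yield is unknown, and if every sample is obtained the gain is zero.

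Second, the plan has other tests. A patient missing month 1 still enters baseline vs month 4, and the reverse. In the assumed scenario that month 4 paired test has power similar to or higher than the proposed joint test. This also stands and limits how much the point matters. It does not make the complete-case version of the three-timepoint test, which the plan itself lists, a good choice.

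Third, the documents never mention dropping incomplete patients. That is correct: it is inferred from how the standard method works, and some software treats unbalanced data differently. Naming the model would settle it.

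Finally, the study is an exploratory pilot with no stated power target, so differences in power have no benchmark to fail. That is a reason to treat this as a cheap improvement and not as a defect that blocks the study.

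**Conclusion.** The point holds for the three-timepoint test on sputum bacterial burden and sputum alpha-diversity. Under the assumptions above, the mixed-model test recovers about 4 percentage points of power at 95% yield, 8 at 90%, 11 at 85% and 16 at 75%, and it needs a weaker missing-data assumption. The main uncertainty is the yield.

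Three stronger readings do not follow:
- A reader might infer that the trial throws away 10–44% of its sputum data. Those shares apply to the three-timepoint test alone; across all planned Hypothesis 1 tests the unused share is 3–19%.
- A reader might infer that the planned ANOVA is biased here. The documents say nothing about which samples will be missing or why, so bias is possible but not shown.
- A reader might infer that any mixed model reproduces the ANOVA on complete data. Only the form given in the fix does.

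**What to change.** For Hypothesis 1 and sputum alpha-diversity, replace the three-timepoint repeated-measures ANOVA with the 2-df joint visit F test from a linear mixed model, specified as follows:
- outcome: log10 normalized copy number, or the diversity index;
- visit as a three-level factor, all available sputum samples, REML;
- compound-symmetry covariance (participant intercept, variance not bounded at zero);
- denominator df within participants: samples − participants − 2, or Kenward-Roger.

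The intercept-and-slope model already planned for beta-diversity should not be copied over, because it is a different test. An unstructured covariance, a chi-square Wald test or a Greenhouse-Geisser-corrected ANOVA will also not match the uncorrected ANOVA on complete data.

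Keep the planned paired t-test or Wilcoxon test on available pairs for baseline vs month 1 and baseline vs month 4. Two-visit contrasts from the random-intercept model can reject 7–8% of the time at a nominal 5% when correlations differ between visits. Report sputum yield by visit.

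The cost is plan wording and slightly more analysis work. Mixed models are already planned for beta-diversity and Hypothesis 3. No patients, samples or procedures are added.

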For Hypothesis 4, which focuses on microbial correlations with clinical outcome measures rather than biomarkers, we will apply same approaches as described for Hypothesis 3. In addition, we will explore the following analysis methods (also applicable to Hypothesis 3): (i) feature-volatility action algorithm, which performs longitudinal feature selection based on random forest regression, implemented in q2-longitudinal in QIIME2; (ii) tools in the R mixOMICS package which bundles access to several sparse multivariate modeling methods that aim to identify key features that explain a biological or clinical outcome of interest.

Related to this, and to leverage tools for examining microbiome data with other -omics/high-dimensional data we will apply tools such as DIABLO (available in mixOMICS package). DIABLO performs data integration coupled with discriminant analysis approach to identify combinatorial features predictive of a binary outcome (e.g., is there a combination of microbial and metabolite features that predict improved asthma control or not? or that associate with an immune biomarker of interest?) As an example, we have recently used DIABLO to explore microbial and metabolite features associated with COPD outcome measures in a multicenter study. In addition, we will determine co-occurrence relationships between microbiota (SparCC [24] or SPIEC-EASI [25]) to identify highly correlated species and determine if 'hubs' of microbiota associate with particular cytokines or metabolites, following by analysis for clustering patterns of microbial-immune relationships [26]. Given the likely heterogeneity of measures in the molecular data types and the small number of subjects, we will apply corrections for multiple comparisons where indicated.

References

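### Hypotheses 3 and 4 are about linked changes and the plan commits to correlating changes, but the listed methods work mainly on levels and none is set up to relate two changes

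*Combined protocol and SAP*

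**What the plan says.** All references are to the combined protocol and SAP.

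**The question.** The first secondary objective (Section III) and Hypothesis 3 relate microbiome changes to immune-marker changes. Hypothesis 4 relates clinical improvement, or its absence, to microbiome changes. Section XII repeats the aim, "whether changes in the airway or gut microbiome correlate with changes in inflammatory markers and immune mediators measured in sputum, blood and NELF", and the Hypothesis 3 analysis opens with "we will examine correlations between change in biomarkers" and changes in the microbiome.

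**The methods listed for Hypothesis 3.**
- (i) "initial correlation analyses performed between paired data at each time point (e.g., specific biomarker dataset vs. microbial ASVs), using Spearman correlations", with q-values for multiplicity.
- (ii) Linear mixed models, illustrated by "levels of immune markers as predictors of post-treatment microbiota diversity or abundances of each microbiota member". On covariates: "fixed effects would include age, sex, BMI, and chronic treatments including corticosteroids or macrolides (type, dose, route").
- (iii) Community-structure tests, "using distance-based PERMANOVA (adonis2) at each time point or in a paired design".
- (iv) High-dimensional methods, described under Hypothesis 4.

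**Hypothesis 4.** "we will apply same approaches as described for Hypothesis 3". The additions are the feature-volatility algorithm (longitudinal feature selection by random forest), mixOmics tools including DIABLO, and co-occurrence networks. The DIABLO example asks "is there a combination of microbial and metabolite features that predict improved asthma control or not".

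No change variable is defined for any marker, taxon, diversity index or clinical score under Hypotheses 3 and 4.

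**The concern.** A correlation across patients at one visit asks whether patients with higher marker values have a different microbiome. Hypotheses 3 and 4 ask whether patients whose markers moved more also had microbiomes that moved more. The two answers can differ in either direction.

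This matters here because the Background already reports a between-patient link: bacterial burden is lower where T2 airway inflammation is higher. A per-visit correlation in this trial could recover that link and be read as dupilumab-induced changes moving together. A real link between changes could equally be buried under stable differences between patients. There is no control arm, so change tracking change is the closest this design comes to tying a microbiome shift to T2 suppression, and even that is only an association.

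**Working it through.** **Is any listed method set up to relate two changes?**
- (i) No. The pairing is marker with taxon inside one visit.
- (ii) Not as illustrated. The predictor is a level. No visit term, baseline value or within/between-patient split is listed, although the wording does not exclude them.
- (iii) Only if the paired option is chosen, and it is not defined.
- Feature-volatility is longitudinal but selects features and does not relate two changes. DIABLO's example outcome is a change, but its microbial and metabolite features are not defined as changes.

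**Inputs.** From the documents: 15 completers and three visits (Section IV). The plan gives no power, alpha, ICC or correlation, so there is no figure of its own to reproduce. Assumed: ICC 0.5/0.7/0.8 (equal for both variables), the correlations below, one marker-readout pair, and two-sided 5% without adjustment.

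**Model.** Each value is a patient effect (variance ICC, between-patient correlation ρb) plus a visit effect (variance 1 − ICC, within-patient correlation ρw).
- Same-visit correlation = ICC·ρb + (1 − ICC)·ρw.
- In a difference between visits the patient effect cancels. Its covariance is 2(1 − ICC)ρw and each variance is 2(1 − ICC), so the change correlation is ρw.

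Example: with ICC 0.7, ρb 0.7 and ρw 0, the same-visit correlation is 0.7 × 0.7 = 0.49 and the change correlation is 0.

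**Simulation** (20,000 trials per cell; Spearman at month 4 against Spearman of month-4-minus-baseline changes; share significant at ICC 0.5/0.7/0.8):

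| ρb, ρw | Same-visit correlation | Same-visit test | Change test |
|---|---|---|---|
| 0.7, 0 | 0.35/0.49/0.56 | 23/42/54% | 5% |
| 0, 0.7 | 0.35/0.21/0.14 | 23/11/8% | about 81% |
| 0.4, 0 | 0.20/0.28/0.32 | 10/16/20% | 5% |
| 0, 0.4 | 0.20/0.12/0.08 | 11/7/6% | 28-29% |
| 0.3, 0.5 | 0.40/0.36/0.34 | 28/24/21% | 44% |
| 0.5, 0.3 | 0.40/0.44/0.46 | 29/34/37% | 18% |
| 0.4, 0.4 | 0.40 throughout | 28-29% | 28-29% |

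With 12 complete pairs, the 81% falls to about 68%.

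**Multiplicity adjustment does not repair the target.** Take 30 markers, 10 linked to one readout, with Benjamini-Hochberg at 5%. Under (0.7, 0), at least one linked marker is flagged in 22/50/68% of trials per visit, against 2-3% for change. Under (0, 0.7), the share of linked markers found is 3/1/0.5% against 57-58%. Under (0, 0.4) it is under 1% against about 5%.

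**Approach (ii) depends on how it is read.** The text fixes neither the marker's visit nor the random effects; a random intercept is assumed here.
- Same-visit markers with a visit term: under (0, 0.7), detection is 83/77/75% with the two post-treatment visits and 98-99% with all three. Under (0.7, 0), it is significant in 29/46/55% and 29/40/45%.
- Baseline marker against a later readout (checked as a Spearman correlation with month 4): about 5% under (0, 0.7), which is chance.
- Same-visit marker split into patient mean and within-patient deviation, three visits with a visit term: 5% under (0.7, 0), 99% under (0, 0.7) and about 59% under (0, 0.4).

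**The case against.** **The plan does commit to a change analysis.** The Hypothesis 3 paragraph opens with it, and (i) is called initial. This stands. A reader might infer that the investigators overlooked change or plan no analysis of it; the documents do not support that. What is missing is the operational step between the stated aim and the tests.

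**The mixed model could do the job.** Partly right. With same-visit markers it detects linked changes well, so it would be wrong to say that every listed method misses them. But unsplit it mixes them with between-patient differences, and with baseline markers it does not test change.

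**The illustration uses extremes.** Fair. In mixed cases the gap is smaller, and with equal correlations it is nil. A significant per-visit result is a false signal only if it is reported as linked change, which the plan does not say it will do. Eligibility requires raised eosinophils or daily oral steroids, which may narrow the T2 contrast. By r·u/√(1 − r² + r²u²), 0.7 falls to 0.40 if the marker's between-patient SD is cut to u = 0.445 of its unrestricted value, so the 0.4 rows may be nearer the truth.

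**This is an exploratory pilot of 15.** True, and power is modest whatever is done. Exploratory status relaxes error control; it does not make a cross-sectional correlation answer a question about change.

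**Level-based models have a use.** Agreed. They suit the secondary objective on predicting clinical improvement from immune and microbial patterns. They need the right label, not removal.

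**Conclusion.** The point holds as a gap between a stated aim and the methods meant to deliver it; it should be fixed. The text alone shows that (i) correlates levels, (ii) is illustrated with levels, (iii) makes pairing optional, and Hypothesis 4 inherits them.

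The size is illustrative because every ICC and correlation is assumed. At the extremes the per-visit test is significant in 23/42/54% of trials when changes are unrelated, and finds 23/11/8% against about 81% when only changes are linked. At 0.3 between and 0.5 within it is 28/24/21% against 44%. At a change correlation of 0.4, even the right test has only about 29% power, and about 5% of linked markers survive Benjamini-Hochberg. The fix therefore corrects the target; it does not make the trial well powered.

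A reader might extend this to Hypotheses 1 and 2. That does not follow: their paired before-after comparisons answer the primary objective.

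**What to change.** In Section XII, Hypothesis 3, carried over to Hypothesis 4:

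1. **Lead test.** Replace the per-visit Spearman as the main analysis with a Spearman correlation of baseline-to-month-4 change in marker or clinical outcome against baseline-to-month-4 change in microbiome readout, with q-values over that family. Use baseline to month 1 as support where both sides are measured. That excludes stool and plasma (no month-1 sample); IgE is measured once and has no change score.
2. **Define change on both sides.** Log-scale difference for cytokines, cell counts and FeNO; raw difference for ACT, mAQLQ and FEV1; difference in CLR abundance, alpha diversity and log10 burden.
3. **Approach (ii) as support, for three-visit measures.** Use same-visit markers, a visit term, and the marker split into patient mean and within-patient deviation; read the within-patient coefficient. Where it applies it is more powerful than the lead test (about 59% against 29% at a change correlation of 0.4), but it cannot serve measures taken only twice.
4. **Approach (iii).** Use the paired form.
5. **Labels.** Call per-visit correlations descriptive, and assign level-based prediction models to the objective on predicting improvement.

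**Cost.** Wording and analysis time only. Table 1 schedules FeNO, nasal fluid, sputum and blood count at all three visits. The Visit 2 text in Section V mentions no blood draw, so confirm that the month-1 count is taken.

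**Downsides.** Change scores are noisier for poorly repeatable markers, and a missing sample loses that patient's change. If between- and within-patient correlations are equal, the split loses power against the unsplit model (59% against 77% at 0.4, three visits).
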